8.5 Physical Examinations, Vital Signs, and Electrocardiograms

The investigator will perform complete or brief physical examinations according to the schedule of activities ([Appendix 2](#)).

Complete physical examinations will be per standard care at the study site and may include dermatologic, cardiac, respiratory, lymphatic, gastrointestinal, musculoskeletal, and neurologic systems, and other systems if clinically indicated by symptoms. Weight will be measured as part of the examination. Height will be measured only at screening.

Brief physical examinations will be directed toward patient-reported symptoms and include investigating any new abnormalities. Weight will be measured as part of the examination.

Vital sign measurements will include temperature, blood pressure, and heart rate.

Standard 12-lead ECGs will be obtained and read locally for study eligibility purposes.

9 ASSESSMENT OF EFFICACY AND SAFETY ENDPOINTS

9.1 Assessment of Efficacy

9.1.1 Assessments for the Primary and Secondary Efficacy Endpoints

The assessment for the primary and secondary efficacy endpoints will include ^{18}F -NaF PET/CT imaging and assessment of disease progression.

9.1.1.1 ^{18}F -NaF PET/CT Imaging

^{18}F -NaF PET/CT imaging will be performed during the study as follows:

- NaF-1: Following screening, within 7 days before first dose
- NaF-2: At week 13
- NaF-3: At the time of PSA, radiographic (bone or soft tissue), or other clinically relevant progression, or at 2 years without progression after treatment initiation

Up to 5 patients at each study site will have a second baseline scan to assess reproducibility of the scans at each study site.

^{18}F -NaF PET/CT imaging will be performed according to the procedures detailed in the imaging instruction manual and interpreted at the central imaging vendor.

9.1.1.2 Assessment of Disease Progression

The assessment of disease progression will include PSA, radiographic (bone and soft tissue), and other clinically relevant events as follows:

PSA progression triggering NaF-3 will be defined as an increase of at least 25% AND an absolute increase of at least 2.0 ng/mL above nadir.

Bone disease progression will be defined as the appearance of at least 2 new lesions after screening assessed by $^{99\text{m}}\text{Tc}$ -MDP bone scintigraphy. Progression at week 13 or earlier will require a confirmatory $^{99\text{m}}\text{Tc}$ -MDP bone scintigraphy at least 6 weeks later showing at least 2 additional new lesions related to prostate cancer (compared with the previous scan). After week 13, no confirmation of progression will be required if at least 2 new lesions related to prostate cancer are observed.

Soft tissue disease will be assessed by CT or MRI obtained at investigator discretion. Radiographic progression for soft tissue disease will be defined by RECIST 1.1.⁷

Other clinically relevant events of progression will be determined by the investigator and may include, but are not limited to, significant bone pain or skeletal-related events.

CCI

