3 INVESTIGATIONAL PLAN

3.1 Overall Study Design and Plan: Description

This phase 2, open-label, single-arm study in patients who are chemotherapy-naïve in the castration-resistant setting with progressive bone-metastatic CRPC is designed to evaluate ^{18}F -NaF PET/CT imaging as a method to quantify changes in total tumor burden in bone metastases in individual lesions as well as across all lesions, and the heterogeneity of response in those bone lesions, after treatment with enzalutamide. The primary endpoint is the proportion of patients with at least 1 responding bone lesion at the time of PSA, radiographic (bone or soft tissue), or other clinically relevant progression or at 2 years without progression after treatment initiation.

The study will enroll approximately 20 patients at 3 study sites in the US. ^{18}F -NaF PET/CT imaging will be performed during the study as follows:

- NaF-1: Following screening, before first dose
- NaF-2: At week 13
- NaF-3: At the time of PSA, radiographic (bone or soft tissue), or other clinically relevant progression, or at 2 years without progression after treatment initiation

Following screening including a $^{99\text{m}}\text{Tc}$ -MDP bone scintigraphy, enrolled patients will have baseline ^{18}F -NaF PET/CT imaging (NaF-1) and then begin open-label treatment with enzalutamide (160 mg) administered as four 40-mg capsules by mouth once daily. PSA response will be determined at week 13 when a second ^{18}F -NaF PET/CT imaging (NaF-2) is obtained. Patients with any increase in PSA at week 13 may discontinue treatment and proceed to safety follow-up unless the investigator considers continuation of study drug to be beneficial. For all continuing patients, PSA will be monitored every 8 weeks after week 13 and other study assessments will continue to be obtained. A third ^{18}F -NaF PET/CT imaging

(NaF-3) and a follow-up ^{99m}Tc -MDP bone scintigraphy will be performed when PSA progression (an increase of at least 25% AND an absolute increase of at least 2.0 ng/mL above nadir), radiographic progression (bone or soft tissue), or other clinically relevant progression (eg, significant bone pain or a skeletal-related event) is observed, or at 2 years without progression after initiation of treatment. No ^{99m}Tc -MDP bone scintigraphy will be required at the time the NaF-3 bone scan is obtained if bone disease progression was confirmed earlier on bone scintigraphy obtained at investigator discretion.

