5.2.5 Week 21 and Repeating Every 8 Weeks

Visits repeat every 8 weeks (\pm 7 days) until criteria are met for permanent treatment discontinuation (Section 5.3). Drug supply must be taken into account if a window is used to schedule the next visit. Assessments are performed at every visit or every other visit as noted.

Week 21 procedures are listed in Table 5.

Table 5: Week 21 and Repeating Every 8 Weeks Procedures

Activity / Assessment / Timing	Comment
General Activities	
Brief physical examination → Perform every 16 weeks (± 7 days)	Measure vital signs (temperature, blood pressure, and heart rate), weight, and ECOG performance status (Table 13). Perform symptom-directed examination and investigate any new abnormalities.
Adverse events review	Record any new or ongoing adverse events.
Concomitant medications review	Record any new medications or changes in ongoing medications.
Enzalutamide dispensing (if applicable)	Provide the patient with an 8-week supply. Provide instructions for dosing, storage, and return of all bottles (used and unused) of study drug at future visits.
Study drug accountability	Record study drug returned and remind patient to return all bottles (used and unused) at each future visit.
Local Laboratory Evaluations	
Serum chemistry, hematology → Perform every 16 weeks (± 7 days)	Refer to analytes listed in Table 12.
PSA	

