3.1. Primary Endpoint

The single primary endpoint is the **proportion of patients with** \geq 1 **responding bone lesion on the third scheduled F-NaF PET/CT scan** for this study. For clarity going forward, this scan will be referred to as NaF. Three such NaF scans are scheduled and are noted below:

| Scan identifier | Scheduled to occur at |
|-----------------|--|
| NaF-1 | Screening |
| NaF-2 | Week 13 |
| NaF-3 | Time of progression, or at 2 years after |
| | treatment start, whichever occurs first* |

* If progression occurs before Week 13, then NaF-3 will constitute the scan at progression and support the primary analysis, even though NaF-2 hadn't occurred yet.

A lesion is considered responding if the change from baseline in total standardized uptake value (SUV(total)) is below the limit of agreement (LOA). The LOA will be estimated based upon test/retest analysis and provided by the vendor.

Protocol MDV3100-18 (C3431012) (Enzalutamide) Statistical Analysis Plan

The NaF-3 will be triggered by the earliest of any of the following events:

- Prostate-specific antigen (PSA) progression:
 - Defined as percentage change from baseline $\geq 25\%$ and nominal increase ≥ 2.0 ng/mL above the nadir (or above the baseline if no decline by week 13).
- Bone disease progression:
 - Defined as ≥ 2 new lesions assessed by bone scintigraphy.
- Soft tissue disease progression:
 - Defined by RECIST v1.1.
- Clinically relevant progression:
 - Defined by the investigator.
- Two years after start of therapy.

[figure not shown]
NaF scans will be interpreted by a central imaging vendor.

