5.2.4. Unscheduled Assessments

Unscheduled assessments will be used when deriving baseline and worst case on-treatment for safety and patient-reported outcome analyses (except where noted for baseline ECGs). Additionally, unscheduled assessments will be used for efficacy analyses (eg, defining date of PSA progression, date of last contact).

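### One unconfirmed PSA reading can trigger NaF-3, so a stable PSA may be labelled progression by noise; the result should also be reported by trigger and by sustained PSA rise

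*Protocol*

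**What the plan says.** Protocol 9.1.1.2 sets the PSA trigger: "PSA progression triggering NaF-3 will be defined as an increase of at least 25% AND an absolute increase of at least 2.0 ng/mL" above nadir. The Synopsis, Protocol 3.1, Table 6 and 10.3.1 repeat it, and so does SAP 2.2. None of these places asks for a second reading. The protocol does not define nadir further and does not say whether the baseline value counts towards it.

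SAP 3.1 words the rule differently. Its 25% limb is "Defined as percentage change from baseline", and only the 2.0 ng/mL limb refers to the nadir ("or above the baseline if no decline by week 13").

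On timing, Protocol 3.1 says "PSA will be monitored every 8 weeks after week 13", and 5.2.5 says "Visits repeat every 8 weeks". SAP 5.2.4 adds: "Additionally, unscheduled assessments will be used for efficacy analyses (eg, defining date of PSA progression".

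For bone progression, 9.1.1.2 does use confirmation early on: "Progression at week 13 or earlier will require a confirmatory" bone scan. After week 13 it drops that requirement.

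Protocol 10.3.1 takes the primary endpoint from NaF-3 and puts men scanned at 2 years without progression in the same proportion as men scanned at progression. Protocol 3.5 states the hypothesis as continuing response in bone when disease progresses by conventional criteria.

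**The concern.** Nadir, read naturally, is the lowest of several noisy readings, so it tends to lie below the true level. Each new reading is compared with that low value, and the comparison is repeated at every visit. A man whose PSA is stable can therefore meet both limbs by chance.

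NaF-3 is done once. If noise sets it off, a scan taken while disease may still be controlled is recorded as a scan at progression. Such a scan is plausibly more likely to show a lesion below baseline, and it would then be read as support for the hypothesis in Protocol 3.5. No readable analysis splits the result by trigger or checks whether the PSA rise lasted.

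**Working it through.** The plan gives no figure to reproduce: the sample size of about 20 is practical, and no false-trigger rate, PSA variation or expected response rate is stated.

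**Inputs from the documents.** Thresholds: 25% and 2.0 ng/mL above nadir (Protocol 9.1.1.2). Scheduled looks before 2 years: weeks 13, 21, ..., 101, that is (101 − 13)/8 + 1 = 12.

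**Assumptions, not in the documents.** True PSA flat from week 13; independent lognormal errors; within-patient CV of 5%, 10% or 15%; plateau of 3, 5, or 10 ng/mL or more; no other trigger first.

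**Step 1: one reading against one earlier reading, 25% limb only.** With σ = √ln(1 + CV²), the chance is 1 − Φ(ln 1.25 / (σ√2)). At CV 10%, σ = 0.0998 and 0.2231/(0.0998 × 1.414) = 1.58, giving 5.7%. At CV 5% it is 0.08%, and at CV 15% it is 14.5%.

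**Step 2: repeated looks against the running minimum.** Simulation of 200,000 men per cell; trigger when a reading is at least 1.25 × nadir and at least nadir + 2.0. Chance of at least one false trigger by week 101:

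| Plateau (ng/mL) | CV 5% | CV 10% | CV 15% |
|---|---|---|---|
| 10 or more | 4% | 81% | 98% |
| 5 | 0% | 11% | 60% |
| 3 | 0% | 0% | 5% |

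By week 53 (6 looks) at 10 ng/mL the figures are 1%, 43% and 74%. Counting a day-1 reading at the same level towards nadir changes little: 4.6%, 84% and 98% at 20 ng/mL.

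The 2.0 ng/mL limb explains the fall at low levels. It binds whenever nadir is below 2.0/0.25 = 8 ng/mL. At a nadir of 5 it requires a 40% rise, and at 3 a 67% rise.

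**Step 3: the SAP 3.1 wording.** With the 25% taken from baseline and a PSA flat at 20 ng/mL, the figures are 0.8%, 29% and 54%. After a five-fold fall from baseline they are 0% at every level and CV tried. Invented values show the conflict: baseline 50, nadir 10, new reading 13. Against nadir the rise is 30% and 3 ng/mL, so the protocol rule is met. Against baseline the change is (13 − 50)/50 = −74%, so the SAP 3.1 rule is not.

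**Step 4: what one later reading achieves.** Tested against the same nadir at a plateau of 10 ng/mL, a fresh independent reading still confirms about 26% of false triggers at CV 10% and 39 to 40% at CV 15%. That is far above the 5.7% and 14.5% of step 1, because the reference is itself an unusually low reading. Accepting either of two later readings raises this to about 42% and 59 to 60%.

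**Step 5: scale of the effect on the pooled proportion.** If a share f of scans is falsely triggered, the shift is f × (difference in response rate). For illustrative values of f from 10% to 40% and differences of 10 to 30 points, it runs from 0.10 × 10 = 1 point to 0.40 × 30 = 12 points. Neither quantity is known. For comparison, 16 responders of 20 has an exact 95% interval of 56% to 94%.

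**The case against.** A reader might infer that the reported proportion does contain men who have not progressed, and that most stable men will trigger falsely. The documents support neither. The high rates need a man flat at about 8 to 10 ng/mL or more for most of two years, a CV of at least 10%, independent errors and no other trigger. Nothing shows how many of about 20 men fit that. Correlated errors would lower the rates, and a flat PSA does not exclude progression in bone or soft tissue.

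A second tempting reading is that the primary estimate is biased upward by a known amount. The endpoint is not a progression-only rate: a false trigger in a stable man may only bring forward a scan that would have counted at 2 years. SAP 6.1 requires a lesion's change to pass a limit of agreement. Since one lesion is enough, the proportion could already be near its ceiling. The direction is plausible; the size is not established.

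Third, the contrast with bone is limited. Bone progression needs no confirmation after week 13, which is the period simulated here.

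Fourth, unscheduled PSAs need not add many looks. Protocol Table 7 and the unscheduled column of Appendix 2 list no PSA, and 8.4 keeps results from a different laboratory used at such visits out of the database. Protocol 5.2.7 does allow diagnostic tests for suspected progression, so some extra readings are possible.

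Fifth, the SAP 3.1 wording would shrink or remove the effect. As an analysis definition that is right, but it does not settle the matter: sites order the scan under the protocol, SAP 2.2 repeats the protocol's rule, and an analysis rule cannot move a scan already taken.

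The study is also exploratory, with estimation as its aim (SAP 5.1). That argues for a supportive analysis and against changing the primary one.

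**Conclusion.** The concern holds in a limited form. The trigger is a single PSA reading against a nadir, looked at 12 times on schedule, so noise can fire it. How often is unknown: under the stated assumptions the chance by week 101 runs from 0% to 98%, depending on CV and PSA level, and the documents give neither.

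Two things are certain from the text. The PSA definitions in SAP 3.1 and in the protocol with SAP 2.2 disagree and must be reconciled. And the pooled proportion mixes men labelled as progressing with men declared progression-free at 2 years, so on its own it does not answer the question in Protocol 3.5. The harm is to that interpretation and to the timing of the scan; any bias is plausibly upward and remains unquantified. Text following Protocol 9.1.1.2 and much of SAP Appendix 4 is blacked out, so the absence of a by-trigger analysis is a statement about the readable text only.

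**What to change.** In SAP 3.1 and 6.1, as an analysis change only:

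1. Reconcile the PSA definition across the protocol, SAP 2.2 and SAP 3.1, and state whether baseline counts towards nadir.
2. Keep the primary analysis. Also report the number, percentage and Clopper-Pearson interval of responders by trigger: PSA only, radiographic, clinical, and 2 years without progression.
3. Flag a PSA-only trigger as sustained when one prespecified later reading also meets the reconciled rule against the same reference. That reading is the first PSA drawn on a later date than the triggering draw and before any new anticancer therapy or treatment stop. If there is none, class the trigger as not assessable. The later date matters because no interval between trigger and NaF-3 is given, so the PSA in Protocol Table 6 may be the triggering draw. The limit on therapy matters because other treatment may be added after NaF-3 (Protocol 7.2). A single reading is named because accepting either of two confirms more false triggers.
4. Report the counts of sustained, not sustained and not assessable triggers. As a supportive result, give the proportion in men with sustained PSA, radiographic or clinical progression.
5. Base statements about response at progression on items 2 and 4, not on the pooled proportion alone.

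Cost: SAP wording, one derived flag and a few table rows, with no new sample or visit. The downsides are small subsets with wide intervals, some true progressors classed as not sustained or not assessable, and only partial removal of false triggers, as step 4 of the working shows.

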9.2 ECOG Performance Status Assessments

ECOG performance status assessments are required to assess patient functional status for study eligibility purposes and will be performed throughout the study according to the schedule of activities (Appendix 2). Details of the assessment are shown in Table 13.

Table 13: ECOG Performance Status Assessments

Score	Description of Functional Status
0	Fully active, able to carry on all predisease performance without restriction
1	Restricted in physically strenuous activity but ambulatory and able to carry out work of a light or sedentary nature, eg, light house work, office work
2	Ambulatory and capable of all self-care but unable to carry out any work activities. Up and about more than 50% of waking hours
3	Capable of only limited self-care, confined to bed or chair more than 50% of waking hours
4	Completely disabled. Cannot carry on any self-care. Totally confined to bed or chair
5	Dead

Source: Oken et al (1982)¹⁰

10 STATISTICAL METHODS AND SAMPLE SIZE DETERMINATION

10.1 Statistical and Analytical Plans

A statistical analysis plan will present the detailed statistical methods and analyses for this study.

10.2 Analysis Populations

The intent-to-treat population is defined as all patients enrolled in the study and will be used for all efficacy analyses unless otherwise specified.

The safety population is defined as all patients who receive any amount of study drug. The safety population will be used for all safety analyses.

10.3 Efficacy Analyses

The primary efficacy endpoint analysis will include patients who undergo NaF-1 and NaF-3 ¹⁸F-NaF PET/CT imaging. CCI

Table 14: Definition of Terms for NaF Uptake Measures

Term	Definition
SUV _{total}	Total NaF uptake, which represents the tumor burden across all (global) bone lesions or in individual lesions reflecting bone-metastatic prostate cancer
SUV _{hetero}	Heterogeneity of NaF uptake, which represents heterogeneity of lesion activity
SUV _{mean}	Mean NaF uptake, which represents the average activity of all lesions
SUV _{max}	Maximum NaF uptake, which represents the activity of the most aggressive lesion
N	Total number of lesions, which represents a numerical sum of all lesions
VF	Volume fraction, which represents the fraction of skeletal involvement

10.3.1 Primary Efficacy Endpoint Analysis

The primary efficacy endpoint is the proportion of patients with at least 1 responding bone lesion (defined as a lesion with an SUV_{total} less than at baseline) on the third ¹⁸F-NaF PET/CT scan (NaF-3) performed for each patient. This assessment will be triggered by any of the following events:

- PSA progression (an increase of at least 25% AND an absolute increase of at least 2.0 ng/mL above nadir)
- Bone disease progression (the appearance of at least 2 new lesions after screening assessed by ^{99m}Tc-MDP bone scintigraphy)
- Soft tissue disease progression defined by RECIST 1.1⁷
- Clinically relevant progression (eg, significant bone pain or a skeletal-related event)
- At 2 years without progression after treatment initiation

10.3.2 Secondary Efficacy Endpoint Analysis

The secondary efficacy endpoint is the heterogeneity of response across all bone lesions as determined by the global SUV_{hetero} at the time the primary endpoint is determined for each patient. The global SUV_{hetero} score is a measure of the heterogeneity of tumor activity across all bone lesions and is defined as follows, where *g* = global, *l* = lesion, *N* = number of bone lesions.

$$gSUV_{hetero} = \frac{\sum_{i=1}^N (lSUV_{mean}^i - gSUV_{mean})^2}{N}$$

In other words, the global SUV_{hetero} score is the sum of the squares of the differences between the SUV_{mean} for each bone lesion and the global SUV_{mean}, divided by the number of lesions. Thus, a higher global SUV_{hetero} score reflects more heterogeneity in bone lesion activity.

CCI

CCI

10.4 Safety Analyses

All safety analyses will be performed using the safety population.

Safety analyses will be summarized. Safety will be evaluated by the incidence of serious adverse events, incidence and severity of adverse events, incidence of permanent treatment discontinuation due to adverse events, and incidence of new clinically significant changes in clinical laboratory values and vital signs.

The treatment-emergent period is defined as the duration of time from the date and time of the first dose of study drug treatment (enzalutamide) through 30 days after the last dose of study drug treatment (permanent treatment discontinuation) or the day before initiation of cytotoxic chemotherapy, a lutamide (bicalutamide, nilutamide, or flutamide), or a new investigational therapy, whichever occurs first.

Adverse events will be coded according to the Medical Dictionary for Regulatory Activities (MedDRA) and tabulated by system organ class and by preferred term within each system organ class. Tabular summaries will include the incidence overall (number and percentage of patients with treatment-emergent adverse events classified by system organ class and preferred term); incidence by intensity (severity graded according to the CTCAE, version 4), causality, seriousness, and outcome (eg, leading to discontinuation of study drug); and other presentations as appropriate.

Serious adverse events occurring before study treatment will be tabulated separately if considered related to study procedure.

Patients with the same adverse event reported more than once will be counted once at the maximum severity or strongest relationship to study drug.

Toxicity for laboratory parameters (hematology, serum chemistry) will be graded using the CTCAE, version 4 when applicable. Shift tables will be provided as appropriate for each parameter to summarize baseline toxicity grade versus postbaseline toxicity grade. For each laboratory parameter that is not gradable by the CTCAE, a shift table based on the normal range (low, normal, and high) will be provided to summarize baseline result versus postbaseline result. For each laboratory parameter, the baseline laboratory value is defined as the last laboratory value collected on or before the date of the first dose of study drug.

